#### Definitions of Adequate Treatment Within 3-month Regimen (Arm 1)

- Taken a total of at least 56 doses of allocated intensive phase treatment within 70 days of starting treatment
- AND taken at least 28 doses of continuation phase treatment within 49 days (7 weeks) of completion of the intensive phase
- AND missed no more than 21 doses of medication overall.

Definitions of Adequate Treatment within 6-month Regimen (Arm 2)

- Taken a total of at least 56 doses of allocated intensive phase treatment within 70 days of starting treatment
- AND taken at least 100 doses of continuation phase treatment within 154 days (22 weeks) of completion of the intensive phase
- AND missed no more than 42 doses of medication overall.

3.2.2 Tolerability

Proportion with premature discontinuation through 65 weeks, defined as discontinuation other than due to violent death, natural disaster, or administrative censoring.

3.2.3 QT interval

We derive the outcome measures defined below from ECG readings, which the site conducts in triplicate (three ECGs 5-10 minutes apart). We will use the mean of all measurements (up to 3) that are readable and available.

3.2.3.1 Mean baseline QTcF and change from baseline in mean QTcF at weeks 2, 8, and end of treatment (EOT) (Arm 1, week 13; Arm 2, week 26)

3.2.3.2 Occurrence of absolute QTcF  $\geq 480$  ms and  $< 500$  ms, and  $\geq 500$  ms, at any time during study treatment

3.2.3.3 Occurrence of QTcF change from baseline of  $\geq 30$  ms and  $< 60$  ms, and  $\geq 60$  ms, at any time during study treatment

3.2.4 Time to stable culture conversion in liquid and solid media through week 65

Defined as the first of two (consecutive or non-consecutive) negative sputum cultures without an intervening positive culture, and/or visits wherein the participant is unable to produce sputum and has no signs of active TB. Conducted separately for liquid and solid media.

3.2.5 Proportion of participants with culture conversion at weeks 8 and 12 across all study arms.

Liquid (MGIT) and solid media analyzed separately.

3.2.6 Time (days) to positivity in liquid culture (MGIT) after start of treatment through week 65

We will report the median (Q1, Q3) times to positivity in liquid culture at each time point (weeks 1, 2, 3, 4, 6, 8, 10, and 12) in Arm 1 and Arm 2.

3.2.7 Change in chest X-ray (CXR) score from baseline to end of treatment (EOT).

Sites conduct the baseline chest X-ray during screening. We will compute the chest X-ray score with the following validated formula (Ralph et al. Thorax 2010):

CXR Score = percent of total lung affected by any pathology + 40 (if cavitation is present).

We will compute the CXR scores based on both site assessment of the chest X-ray and an assessment by independent central reviewers blinded to study treatment.

- 3.2.8 Proportion of participants with one or more serious adverse events (SAEs) through week 65
- 3.2.9 Proportion of participants who have a TB relapse from EOT until week 65  
For participants who had successful culture conversion through the end of study treatment, TB relapse is defined as a recurrence of TB emanating from the same strain as the participant's originally diagnosed TB, which will be determined through molecular genotyping.

- 3.2.10 Proportion of participants who have a TB recurrence from EOT until week 65
- 3.2.11 Plasma pharmacokinetic parameters for CFZ

Arm 1

We will report the minimum concentration (Cmin), maximum concentration (Cmax), time of Cmax (Tmax), and area under the concentration curve (AUC0-24h) estimated through non-compartmental analysis for weeks 2 and 13 summarized separately.

Arm C

We will report the estimated minimum concentration (Cmin), maximum concentration (Cmax), time of Cmax (Tmax), and area under the concentration curve (AUC0-24h) estimated through non-compartmental analysis for week 2.

Arm 1 versus Arm C

We will compare the estimated minimum concentration (Cmin), maximum concentration (Cmax), time of Cmax (Tmax), and area under the concentration curve (AUC0-24h) at week 2 between Arm 1 and Arm C intensive PK participants. We will estimate the geometric mean ratio comparing Arm 1 to Arm C and corresponding 90% confidence interval. As a supplemental analysis, we will use a Wilcoxon rank sum test and report the p-value.

3.2.12 Change from baseline in skin pigmentation (colorimetric L\*, a\*, b\* parameters) utilizing ambient light-independent reflectance mapping at weeks 8, 13, 26, and 65.

Mean change in total color difference from week 0 to each of weeks 8, 13, 26, 65 in Arm 1 vs Arm 2 at each of the following locations; (1) left cheek, (2) right cheek, (3) forehead, (4) chin.

Mean change in total color difference from week 0 to each of weeks 8, 13, 26, 65 in Arm 1 vs Arm 2 using, for each participant, the location with the maximum change.

3.2.13 Change from baseline in participant-reported changes in skin pigment and distress related to perceived skin hyperpigmentation at weeks 8, 13, 26, and 65.

Mean subjective 'change in coloration' score between week 0 and weeks 8, 13, 26, and 65 in Arm 1 vs Arm 2 (10-point numeric rating scale where 0=none, 10=most significant possible).

Mean subjective 'distress related to skin coloration' score at each of weeks 0, 8, 13, 26, and 65 in Arm 1 vs Arm 2 (10-point numeric rating scale where 0=none, 10=worst possible)

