- Up to 117 weeks.
- 65 weeks for participants who are or have been diagnosed with TB treatment failure or recurrence and are or have been referred to six months of local SOC treatment by the national/local TB program.

Arm 2: 65 weeks

Arm C: 65 weeks

3. Section SCHEMA, REGIMEN

The following paragraph has been included to add three months of rifampicin/isoniazid for Arm 1 participants who are currently receiving the experimental 3-month treatment regimen as of 16Jun2023. The treatment regimen for all other participants will remain the same.

Arm 1 participants receiving the experimental 3-month treatment regimen as of 16Jun2023:
rifapentine/isoniazid/pyrazinamide/ethambutol (PHZE) + clofazimine (CFZ) 300 mg once daily for 2 weeks; then PHZE + CFZ 100 mg once daily for 6 weeks; then rifapentine/isoniazid/pyrazinamide (PHZ) + CFZ 100 mg once daily for 5 weeks; then rifampicin/isoniazid (RH) for 13 weeks for a total of 26 weeks of study treatment.

4. Section 1.4, Exploratory Objectives

The following objective has been added to align with the addition of Drug-Susceptibility Testing and Sputum AFB Smear and Culture at weeks 91 and 117:

1.4.8 To explore long term outcomes in Arm 1 participants through 117 weeks after randomization.

5. Section 3.0, STUDY DESIGN

The following update to the Arm 1 regimen and follow-up has been added to the end of the section:

Updates following the DSMB reviews in April and June 2023

Following the DSMB reviews in April and June 2023, and the premature closure to accrual of the study, Arm 1 treatment duration and follow-up was revised for participants who are currently on or have completed Arm 1 study treatment without experiencing treatment failure or TB recurrence, and have not already been referred to six months local SOC treatment. Participants in Arm 1 who have not already been referred to six months local SOC treatment will have follow-up extended through week 117.

6. Section 6.1, Schedule of Evaluations

A new Table 6.1-2 has been inserted for the additional visits and assessments for Arm 1 after week 26. The SOE table for Arm C has been renumbered to Table 6.1-3.

Table 6.1-2: Schedule of Evaluations for Arm 1 Who Have Not Been Referred to Local SOC, Additional Visits and Assessments After Week 26

| Evaluation | Follow-up | | | | | | | | | After Week 65 | |

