## 2 Study Overview

### 2.1 Overview of Study Design

A5362 is an open-label, randomized phase IIc study to evaluate whether a 3-month regimen of rifapentine/isoniazid/pyrazinamide/ethambutol (PHZE) with clofazimine (CFZ) dosed as 100 mg daily with a 2-week 300 mg daily loading dose is superior to the standard of care (SOC) 6-month regimen of rifampin/isoniazid/pyrazinamide/ethambutol (RHZE) for DS-TB with respect to (1) early bacteriologic efficacy defined as time to culture conversion by 12 weeks post-randomization and (2) safety over 65 weeks.

Participants will be randomized to one of three treatment arms; Arm 1 with treatment for 13 weeks (including a 2-week CFZ loading dose of 300 mg daily; Arm 2 with treatment for 26 weeks; or Arm C with treatment for 4 weeks with an experimental regimen and the remaining 22 weeks with SOC (PK subgroup)).

- Arm 1 (Experimental): PHZE + CFZ 300 mg once daily for 2 weeks, PHZE + CFZ 100 mg once daily for 6 weeks; then PHZ + CFZ 100 mg once daily for 5 weeks
- Arm 2 (SOC): RHZE for 8 weeks; then RH for 18 weeks
- Arm C (PK subgroup): PHZE + CFZ 100 mg once daily for 4 weeks; then on study, off study medications and treated according to SOC (RHZE for 4 weeks; RH for 18 weeks)

We will follow all participants in Arms 1, 2, and C from randomization to week 65 for the primary and secondary objectives. Protocol v2.0 LOA #1 also includes extended follow-up for some participants corresponding to new exploratory objectives which will be detailed in a separate SAP.

Participants who consent to intensive PK sampling visits will be randomized to Arms 1, 2, or C in a 2:1:1 ratio, respectively, while participants who do not consent to intensive PK sampling will be

randomized only to Arms 1 or 2 in a 2:1 ratio, respectively. We will stratify randomization based on HIV status and the presence of advanced disease as determined by chest X-ray. We will balance randomization by institution.

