#### 5.1.3.2 QT Prolongation (Objective 2.3.2.3; Outcome Measures 3.2.3.1, 3.2.3.2, 3.2.3.3)

We will compare the mean change in QTcF from screening to weeks 2, 8, and 13 (3.2.3.1) between Arm 1 and Arm 2 in the safety set using a GEE model with exchangeable correlation structure and time by treatment interaction terms (treating time as a categorical variable).

We will compare the change from baseline in QTcF over time between arms using a linear mixed effects model. Randomization arm and week (time) will be fixed effects and participant ID will be a random effect.

We will compare the odds of participants having maximum occurrence of absolute QTcF  $\geq 480$  ms and  $<500$  ms, or  $\geq 500$  ms (3.2.3.2) between Arm 1 and Arm 2 in the safety set using a proportional odds model, if the proportional odds assumption is satisfied. We will assess the proportional odds assumption using the score test for the proportional odds assumption implemented in SAS PROC LOGISTIC. If the score test indicates a statistically significant result at the 0.05 level, we will also assess the proportional odds assumption graphically to confirm. If graphical evidence suggests the proportional odds model is valid, we will use it for analysis.

If the proportional odds assumption does not hold, we will instead estimate the difference in binomial proportions and 95% confidence intervals for the collapsed category of QTcF  $\geq 480$  ms (including QTcF  $\geq 500$  ms), and separately for the category QTcF  $\geq 500$  ms.

The analysis of outcome measure 3.2.3.3 will follow the same approach as that of 3.2.3.2.

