### 6.5 Adverse Events

- Summary of post-entry reportable adverse events according to Section 7 of the protocol
- Summary of post-entry SAE
- Summary of QTcF at screening, weeks 2, 8, and 13
- Summary of difference in QTcF between screening, and weeks 2, 8, and 13
- Proportion with a maximum occurrence of QTcF  $\geq 480$  ms and  $< 500$  ms, and  $\geq 500$  ms

- Proportion with a maximum change from screening of QTcF  $\geq 30$  ms and  $< 60$  ms, and  $\geq 60$  ms, at any time during study treatment
- Summary of Grade 3 or higher post-entry QT prolongation adverse events

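### The QTcF threshold outcomes have no common time window across arms, and the SAP places the Arm 2 end-of-treatment QTcF at week 26 in one section and analyses week 13 in others

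*SAP*

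**What the plan says.** SAP 3.2.3 defines three QT outcomes. Outcome 3.2.3.1 is mean QTcF at baseline and its change "at weeks 2, 8, and end of treatment (EOT) (Arm 1, week 13; Arm 2, week 26"). Outcomes 3.2.3.2 (absolute QTcF) and 3.2.3.3 (change from baseline) are threshold categories counted "at any time during study treatment".

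The analysis section, 5.1.3.2, uses different weeks: "We will compare the mean change in QTcF from screening to weeks 2, 8, and 13", in a GEE model with time as a category. A second, linear mixed model for change over time names no weeks. For the thresholds the text reads "We will compare the odds of participants having maximum occurrence of absolute QTcF" in the stated bands. It uses a proportional odds model with a difference in proportions as fallback, and states no time limit or adjustment for the number of readings.

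The report contents follow the analysis section. Section 6.5 lists "Summary of QTcF at screening, weeks 2, 8, and 13", and 6.7 has contrasts to the same weeks. No QT item in 5.1.3.2, 6.5 or 6.7 names week 26.

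SAP 2.1 gives the treatment windows: "Arm 1 with treatment for 13 weeks" and "Arm 2 with treatment for 26 weeks". LOA #1, item 3, changes this for Arm 1 participants on the 3-month regimen as of 16 June 2023: "then rifampicin/isoniazid (RH) for 13 weeks for a total of 26 weeks of study treatment". SAP version 3.0 was revised to align with that letter, but 3.2.3 still places the Arm 1 end of treatment at week 13 and does not say whether the added weeks count.

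**The concern.** There are two linked faults.

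First, the outcome definition includes an Arm 2 week-26 value that no QT analysis names, and the analysis uses an Arm 2 week-13 value that the definition omits.

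Second, a participant's maximum category cannot fall as readings are added. If "at any time during study treatment" lets in more readings in Arm 2 than in Arm 1, the control proportion rises for a reason unrelated to drug. Objective 2.3.2.3 aims to detect a clofazimine-associated QT increase, so this pushes the comparison toward no difference, which is the unsafe direction for a safety outcome. The primary report includes data until the last enrolled participant completes week 26 (SAP 2.1), so Arm 2 readings late in treatment would be available to enter the maximum.

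The SAP guards against this elsewhere. For Grade 3 or higher adverse events (5.1.1) and SAEs (5.1.3.5) it adds week-13 and week-26 horizons applied to both arms. The QT threshold outcomes have no such horizon.

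**Working it through.** The documents give no event rate, power or sample size for the QT outcomes, so there is no plan figure to reproduce.

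**Windows (SAP 2.1; LOA #1 item 3).** Arm 1: 2 + 6 + 5 = 13 weeks. Arm 2: 8 + 18 = 26 weeks. Extended Arm 1: 13 + 13 = 26 weeks.

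**Scheduled on-treatment readings.** The ECG schedule for the main study is not in the text available, so two readings of the SAP are carried forward:

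- Reading A: 3.2.3.1 and 5.1.3.2 both hold for Arm 2. Arm 2 then has weeks 2, 8, 13 and 26 (4 readings) and Arm 1 has weeks 2, 8 and 13 (3 readings).
- Reading B: 3.2.3.1 is the whole Arm 2 schedule. Arm 2 then has weeks 2, 8 and 26, so readings are 3 v 3, and the week-13 contrast in 5.1.3.2 and 6.7 has no Arm 2 value.

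**Size under reading A.** Let q be the chance that one ECG crosses the threshold, the same in both arms (assumed). With k independent readings, the chance of at least one crossing is 1 − (1 − q)^k. At q = 2%: 1 − 0.98³ = 5.9% and 1 − 0.98⁴ = 7.8%. The correlated columns give each reading a normal latent variable with pairwise correlation 0.5 (assumed).

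| q (assumed) | Independent: 3 v 4 readings | Gap (points) | Correlation 0.5: 3 v 4 readings | Gap (points) |
|---|---|---|---|---|
| 0.5% | 1.5% v 2.0% | 0.5 | 1.4% v 1.8% | 0.4 |
| 2% | 5.9% v 7.8% | 1.9 | 5.1% v 6.4% | 1.3 |
| 5% | 14.3% v 18.5% | 4.3 | 11.8% v 14.4% | 2.6 |
| 10% | 27.1% v 34.4% | 7.3 | 21.8% v 25.9% | 4.0 |

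Gaps are taken before rounding.

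**Effect on a real contrast.** Take the planned 110 v 55 participants (SAP 2.4), two-sided alpha 0.05, an Arm 1 proportion of 20% (assumed), q = 2% in Arm 2 and independent readings. Power is 0.69 with 3 Arm 2 readings and 0.53 with 4. Enrolment at early closure is not given, so this only illustrates the effect.

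A simulation of maximum change of at least 30 ms assumed a clofazimine effect of 10 to 20 ms, a within-person SD of 8 to 12 ms and a between-person SD of 6 to 10 ms. One extra Arm 2 reading cut the Arm 1 minus Arm 2 difference by about 0.6 to 2.4 points. The difference stayed positive in every case.

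**Check of the remedy.** Under reading A, cutting both arms at week 13 gives 3 v 3, or 5.9% in each arm at q = 2% with no drug effect. Under reading B the same cut leaves 3 readings in Arm 1 and 2 in Arm 2: 5.9% v 1 − 0.98² = 4.0%. The imbalance then reverses, so the remedy must depend on the actual schedule.

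**The case against.** An on-treatment window is a defensible choice for a safety outcome, and these outcomes are secondary. The GEE compares mean change at weeks 2, 8 and 13 in both arms, so its estimates do not depend on window length. Grade 3 or higher QT prolongation events are also summarised separately (6.5). The one schedule written into an outcome definition gives 3 v 3 readings, in which case the thresholds carry no scheduled imbalance. All of this stands and limits the point to the threshold outcomes and the conflicting weeks.

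A reader might infer that the Arm 2 maximum builds up over twice the time and so has twice the opportunity. The calendar ratio is indeed 26/13 = 2, but a maximum grows with readings taken, not with weeks elapsed. The documents support 3 v 3 or at most 4 v 3 scheduled readings. Doubling would need many additional ECGs in weeks 14 to 26, and nothing in the text shows them.

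A reader might also infer that a clofazimine effect would be hidden. The figures show dilution and some loss of power, not reversal, and they rest on assumed rates.

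Nor is 13 v 26 weeks uniform. If the LOA #1 extension counts as study treatment, some Arm 1 participants also have 26 weeks. That could narrow the imbalance between arms, but it makes the window differ within Arm 1. It is a further reason to state a cut-off, not evidence that the arms are balanced.

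**Conclusion.** The point holds in limited form. The conflict between 3.2.3.1 and 5.1.3.2, 6.5 and 6.7 is on the page and needs reconciling whatever the ECG schedule is. The lack of a common window for 3.2.3.2 and 3.2.3.3 is also certain from the text.

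Its effect depends on a schedule that the available text does not show. If Arm 2 has ECGs at both weeks 13 and 26, the bias is toward no difference and modest: about 2 points at an assumed 2% risk per ECG and about 4 points at 5% with independent readings, and roughly 1 and 3 points with correlation 0.5. If Arm 2 has only weeks 2, 8 and 26, there is no scheduled excess, and the fault is a week-13 contrast without control data. The change is worth making because it costs little and removes an avoidable bias in a safety comparison.

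**What to change.** 1. Reconcile 3.2.3.1 with 5.1.3.2, 6.5 and 6.7, so that the Arm 2 QTcF weeks in the definition are those analysed and reported. State which weeks enter the linear mixed model.
2. Define the between-arm comparison for 3.2.3.2 and 3.2.3.3 over the same named ECG weeks in both arms. Use weeks 2, 8 and 13 if the schedule has an Arm 2 week-13 ECG, and otherwise only the on-treatment weeks that both arms share. Carry the same window into the threshold items in 6.5 and 6.7.
3. State that ECGs from the LOA #1 extension period, and any unscheduled ECGs after the common cut-off, do not enter that comparison.
4. Report maxima through end of treatment by arm as supplementary, with the number of readings per participant.

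The cost is SAP wording, with no new data. The downside is that later ECGs leave the formal comparison and are only described. If the shared weeks are only 2 and 8, the comparison also loses the Arm 1 week-13 reading, which would then appear only in the supplementary summary.

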#### 4.1.1 Analysis set definitions

##### 4.1.1.1 Analysis sets (used for primary (5.1.1) and key secondary (5.1.2) estimands):

- **Efficacy Set:**  
All participants who are randomized to study treatment and are not late exclusions.  
(Participants will be late exclusions if they do not have any positive culture (liquid or solid) at screening, entry, or week 1, or if they have TB that is RIF-resistant or INH-resistant identified at screening or entry.)
- **Safety Set:**  
All participants who start assigned study treatment.
- **Start treatment/not late exclusion set:**  
All participants who start assigned study treatment and are not late exclusions.
- **Alive/adequate treatment set:**  
All participants who complete an adequate course of treatment as defined within Sections 10.2.5 and 10.2.6 of the protocol and who do not die during treatment.
- **Per protocol Set:**  
All participants who start and complete assigned study treatment.

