## **2.3 Study Objectives**

This Primary SAP addresses the following primary and secondary objectives listed in the study protocol. We address other study objectives outlined in the protocol in subsequent secondary analysis plans.

We will analyze the primary efficacy objective below (2.3.1.1) using a superiority framework based on a one-sided 0.05 alpha level test. For analyses of other objectives, we will present estimates of the parameter of interest alongside their respective two-sided confidence intervals, as specified in Section 5.

We will finalize all analyses for the primary analysis report once the last enrolled participant has completed the week 26 study visit and all queries have been resolved.

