## 2.4 Overview of Sample Size Considerations

We plan to enroll a total of 185 participants; approximately 110 in Arm 1, 55 in Arm 2, and 20 in Arm C. We estimate that we will have at least 90% power to detect an effect between Arm 1 and Arm 2 with respect to the primary efficacy outcome. We assume 70% culture conversion by week 12 in Arm 2 and a hazard ratio of 1.8. We use a 2:1 allocation ratio and assume that 10% of participants will have unevaluable culture conversion results.

For the primary safety outcome, we will compare proportions of participants with any Grade 3 or higher adverse events (AE) between Arms. Table 10.4-2 from the study protocol (copied below) gives the power we would have to detect that Arm 1 is inferior to Arm 2 assuming a two-sided type 1 error of 0.10, 10% probability of developing an AE in the SOC Arm, and varying probabilities (15-30%) of developing an AE in experimental Arm. We also provide the 90% confidence interval (CI) width for the comparison.

Protocol Table 10.4-2

Power	N1	N2	N	Arm 1 Proportion with $\ge$ Grade 3 AE	Arm 2 Proportion with $\ge$ Grade 3 AE	Two-sided type 1 error	90% CI Width
0.13	100	50	150	0.15	0.10	0.10	0.210
0.36	100	50	150	0.20	0.10	0.10	0.218
0.64	100	50	150	0.25	0.10	0.10	0.225
0.85	100	50	150	0.30	0.10	0.10	0.230

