### 3 Outcome Measures

#### 3.1 Primary Outcome Measures

##### 3.1.1 Early Efficacy

Time to stable culture conversion in liquid media, defined as the first of two (consecutive or non-consecutive) negative sputum cultures without an intervening positive culture, and/or visits wherein the participant is unable to produce sputum and has no signs of active TB, up to 12 weeks post-randomization.

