#### **5.1.3.4 Proportion with culture conversion at week 8 and 12 (Objective 2.3.2.5; Outcome Measure 3.2.5)**

We will compare the proportion of participants with stable culture conversion by week 8 and week 12 between Arm 1 and Arm 2 in the efficacy set. We will analyze liquid and solid cultures separately. We will present the difference in proportions and exact 95% confidence intervals.

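### The efficacy set accepts a positive culture in either medium, but conversion is scored one medium at a time, so participants never positive in the scored medium count as early converters and dilute the effect

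*SAP*

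**What the plan says.** SAP 4.1.1.1 defines the efficacy set as randomised participants who are not late exclusions. On culture, the rule is: "Participants will be late exclusions if they do not have any positive culture (liquid or solid) at screening, entry, or week 1". One positive in either medium is enough. The late-exclusion summary in SAP 6.1 repeats the rule without naming a medium.

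The conversion outcomes are medium-specific:

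- Primary (3.1.1): "Time to stable culture conversion in liquid media, defined as the first of two (consecutive or non-consecutive) negative sputum cultures", with no positive in between. Section 5.1.1 analyses this in the efficacy set.
- Time to conversion in both media (3.2.4): "Conducted separately for liquid and solid media". Section 5.1.3.3 carries over the 5.1.1 approach for each medium, censoring at week 26.
- Conversion by weeks 8 and 12 (5.1.3.4), again in the efficacy set: "We will analyze liquid and solid cultures separately".

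Under 5.1.1, a visit with no sputum and no signs of active TB counts as a negative culture. Participants who have not converted and whose cultures are contaminated or missing are censored at the last valid result. Section 5.1.1 lists no sensitivity analyses for the primary efficacy estimand, and its supplemental analyses do not restrict by medium.

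**The concern.** The gate into the analysis and the event inside it use different evidence. Someone who qualified on a liquid culture, never grew on solid, and then gives two valid negative solid cultures is recorded as a solid-media converter at the first post-entry visit. The mirror case, qualifying on solid and never growing in liquid, produces a liquid converter. Neither had anything to convert in that medium, so the event says nothing about the regimen.

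These events should occur in both arms at about the same rate. They raise the conversion proportion in each arm and shrink the contrast between arms. The SAP reports the hazard ratios and the week 8 and 12 differences as estimates with confidence intervals, so the dilution matters even where no test is made. For the primary outcome it also costs power.

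**Working it through.** **Inputs from the SAP.** Section 2.3: "using a superiority framework based on a one-sided 0.05 alpha level test". Section 2.4: "We plan to enroll a total of 185 participants; approximately 110 in Arm 1, 55 in Arm 2, and 20 in Arm C"; "We assume 70% culture conversion by week 12 in Arm 2 and a hazard ratio of 1.8"; 2:1 allocation; 10% unevaluable. Visit weeks 1, 2, 3, 4, 6, 8, 10 and 12 are those listed in 3.2.6. **Assumed:** p, the share of each arm never positive in the scored medium and scored as converting at week 1.

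**Step 1: reproduce the stated power.** Section 2.4 says: "We estimate that we will have at least 90% power to detect an effect between Arm 1 and Arm 2".

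- Arm 1 conversion by week 12 = 1 - 0.30^1.8 = 0.8855.
- Expected events = 0.9 × (110 × 0.8855 + 55 × 0.70) = 122.3.
- Schoenfeld: z = √(122.3 × 2/3 × 1/3) × ln 1.8 - 1.645 = 5.213 × 0.5878 - 1.645 = 1.42, so power is 92.2%.

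The stated figure reproduces. Simulating conversion times read at the listed visits gives 90%.

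**Step 2: add participants with nothing to convert.** Average conversion is (2 × 0.8855 + 0.70)/3 = 0.8237. With 165 × 0.9 = 148.5 evaluable:

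- Informative events per participant = (1 - p) × 0.8237; uninformative events = p.
- Diluted log HR ≈ ln 1.8 × informative events / all events.

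At p=10%: informative 0.7413, all 0.8413, total events 148.5 × 0.8413 = 124.9. Log HR = 0.5878 × 0.7413/0.8413 = 0.518, so HR = 1.68. Power is 86.1%.

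If those participants are left out, events = 148.5 × 0.7413 = 110.1 at HR 1.8, and power is 89.7%.

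| p | Formula: HR / power | Simulation A: HR / power | Simulation B: HR / power | Left out, formula: power |
|---|---|---|---|---|
| 0% | 1.80 / 92.2% | 1.80 / 90% | 1.78 / 89% | 92.2% |
| 5% | 1.74 / 89.5% | 1.73 / 88% | 1.76 / 91% | 91.0% |
| 10% | 1.68 / 86.1% | 1.66 / 83% | 1.67 / 85% | 89.7% |
| 20% | 1.57 / 77.5% | 1.59 / 77% | 1.57 / 75% | 86.4% |

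Simulation A: 3,000 trials per row, 99 v 50, median HR. Simulation B: 600 trials per row, 100 v 50, mean HR. Both use Cox models with Efron ties. The Monte Carlo standard error of power in B is √(0.9 × 0.1/600) = 1.2 points, so its rise from 89% to 91% between the first two rows is noise.

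Leaving these participants out gains 91.0 - 89.5 = about 1.6 points (before rounding) at p=5%, 3.6 at 10% and 8.8 at 20%. By formula, power passes below 90% somewhere between p=3% (90.6%) and p=5% (89.5%).

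The table takes the 70% as applying to participants who can convert. If the 70% already includes the never-positive, simulation A gives 1.73 / 87%, 1.68 / 83% and 1.56 / 71% at p=5%, 10% and 20%.

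**Step 3: week-12 difference.** In each arm the proportion becomes p + (1 - p) × conversion, so the difference is (1 - p) × (0.8855 - 0.70) = (1 - p) × 18.5 points: 17.6 at p=5%, 16.7 at 10% and 14.8 at 20%.

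**The case against.** Several points on the other side stand.

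- **The share is unknown and may be small.** No figure for p appears for either medium. In liquid, below 5% is plausible, and the primary analysis then barely moves.
- **The power figures belong to the liquid primary only.** SAP 2.3 treats the solid outcomes as estimates with confidence intervals, with no power claim. The week-26 analysis was not modelled. Accrual closed permanently and early, and the documents give no final enrolment.
- **The direction is conservative.** Dilution toward no difference cannot manufacture superiority.
- **One set for both media is a defensible estimand choice.** The target population in 5.1.1 is people with confirmed pulmonary TB, whichever medium grew, and a common denominator has value.
- **Restriction can discard real information.** A rule limited to screening and entry would drop people first positive in that medium at week 1. Removing 5% who were in fact informative takes power from 92.2% to 91.0%.
- **A coding rule may exist elsewhere.** SAP 1.1 places coding descriptions in the Analysis Implementation Plan, and the protocol as supplied is only the Letter of Amendment.

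A reader might also infer that anyone with a negative or contaminated baseline liquid culture is a false converter. The text does not support that. A contaminated culture is not scored as a negative, and such a participant may grow at a later visit and convert properly after that. Only those truly never positive, with valid negatives or no sputum and no signs of TB, are affected.

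What remains is that the SAP's written rule, followed literally, records a conversion where there was none. How the analysis set matches the event belongs in the SAP.

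**Conclusion.** The mismatch is real on the supplied text, and its direction is clear: toward no effect, in the hazard ratios and in the week 8 and 12 differences, without inflating type I error. Its size depends on p. For the liquid primary at planned size, the HR falls to about 1.73-1.76, 1.66-1.68 and 1.57-1.59 at p=5%, 10% and 20%, with power about 88-91%, 83-86% and 75-78%. It is negligible when p is small. These ranges assume exponential conversion times, equal p in both arms, and 70% conversion among those able to convert.

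Two stronger readings are not supported. The first is that the primary analysis is materially underpowered for this reason; that needs a value of p that the documents do not supply. The second is that the false conversions are exactly balanced between arms. Balance holds only in expectation, and because a week 1 culture can qualify a participant after randomisation, the regimen could affect inclusion slightly.

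The solid-media outcomes may be the more exposed, because qualifying on liquid alone is enough to enter them. The loss there has not been quantified.

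**What to change.** - **Solid media (5.1.3.3 and 5.1.3.4):** analyse conversion in efficacy-set participants with at least one positive solid culture at screening, entry or week 1, the window 4.1.1.1 already uses. Because week 1 follows randomisation, repeat the analysis with screening and entry only as a check.
- **Primary liquid outcome (5.1.1):** keep the efficacy set as it is. Where the plan now lists no sensitivity analysis, name one limited to participants with a positive liquid culture in the same window.
- **Reporting (6.1):** give the number left out, by arm and medium. This also shows the actual p, and so whether the dilution matters.

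If the Analysis Implementation Plan already has such a rule, moving it into the SAP is enough.

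The cost is a few sentences, using cultures already collected. The downside is a slightly smaller denominator that differs between liquid and solid.
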